## 7. Safety reporting

### 7.1 Section 10 WMO event

In accordance to section 10, subsection 1, of the WMO, the investigator will inform the subjects and the reviewing accredited METC if anything occurs, on the basis of which it appears that the disadvantages of participation may be significantly greater than was foreseen in the research proposal. The study will be suspended pending further review by the accredited METC, except insofar as suspension would jeopardize the subjects' health. The investigator will take care that all subjects are kept informed.

### 7.2 Possible (serious) adverse events and suspected unexpected serious adverse reactions

The ALA patches are already used in and approved for the therapy of benign skin disorders with Photodynamic Therapy (PDT). Its use is safe and provides good treatment results with excellent cosmetic outcome. The 2x2cm large Alacare patches (8mg) were developed by Photonamic and are marketed for the treatment of actinic keratosis, a benign skin disorder, with photodynamic therapy. In dermatology, its use has been investigated. In phototherapy, the treatment effect depends on the production of singlet oxygen by photoactivation of PpIX. Excitation of PpIX induces apoptosis in cells as a result of oxygen-radical formation. In general, this requires illumination with continuous light and a high cumulative light dose. In contrast, PpIX-TSLT uses short-pulsed excitation and a total light dosage, i.e., orders of magnitude less than used for photodynamic therapy. A recent systematic review showed no significant (serious) adverse effects of ALA patches.

Side effects of ALA described with photodynamic therapy are burning of the skin (<50%, resolved in 1-4 days), burning sensation of the skin (<92%), pruritus, hyperpigmentation (22-36%), edematous lesion (35%), application site erythema (92-99%), local pain (1-92%, <30% severe), application site irritation (72%), local haemorrhage(1-4%), and headache (<10%). Most of these reactions resolved within 2 weeks. There are no reported (serious) adverse events. Since the light load at the cutaneous-PpIX-TSLT is much lower than in phototherapy, no adverse events are expected. While PpIX-TSLT is likely to be safe, the effects of phototoxicity after PpIX induction should always be considered a potential risk requiring a risk and safety assessment in any intended application.

### 7.3 Adverse events (AEs)

Adverse events are defined as any undesirable experience occurring to a subject during the study, whether or not considered related to the investigational product. All adverse events reported spontaneously by the subject or observed by the investigator or his staff will be recorded.

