## 5. Methods

### 5.1 Study procedures

#### 5.1.1 General

Since research has shown that approximately 10% of critically ill patients can make autonomous decision regarding research participation, most decisions will be made by their substitute decision makers, who are already overwhelmed by the medical information of the patient itself. Furthermore, studies have shown that obtaining contact with their substitute decision makers can be difficult in 7%, no decision maker exist in 6% of the cases. In addition, approximately half of the opportunities to recruit patients are missed because of workload and narrow time windows for inclusion. Difficulties in recruitment of eligible patient can lead to delayed identification of (in)effective treatment/diagnostics and limitation of generalizability. Alternative consent models are therefore needed to improve recruitment and minimize withdrawal. Therefore, we will first ask all ICU patients admitted to the ICU, or their legal representatives, expected to stay at the ICU for longer than 24 hours for participation in our study. Patients admitted to the cardiothoracic department which will be admitted to the ICU post-operatively, will be asked for an informed consent on the day before the cardiothoracic operation. An information leaflet will be given and informed consent will be sought. Patients or their legal representatives will be told that a person can only participate in the study if he/she meets the inclusion criteria. However, if no legal representative could have been reached in person for written informed consent, while the patient meet the eligibility criteria, the patient will be included in the study and deferred informed consent will be sought within 48 hours after oral consent has been given. If written informed consent is available or oral consent given, at the moment the decision is made to administer a red cell transfusion, the self-adhesive ALA-patch will be placed. Due to logistics, the normal time elapsing between the decision of a non-emergency red cell transfusion and the actual administration is 2 to 3 hours. The induction time of PpIX is at least 4 hours, therefore red cell transfusion will be delayed by 1 to 2 hours. At no time red cell transfusion will be delayed in order to have enough time to induce PpIX if the patient is clinically in need of a red cell transfusion. To ensure this, the clinician responsible for the patient, and not the researcher, has the final decision in the timing of the red cell transfusion.

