### 5.4.2 Secondary outcomes

Secondary study outcomes include:

- Value of mitoPO2 measurements in predicting (ischemic) organ damage. The following parameters for organ damage (that are routinely collected) will be assessed: lung (pO2/FiO2 ratio), heart (troponin, CK, an ECG, CI), renal (creatinine, urine production, glomerular filtration rate, RIFLE classification), brain (delirium, RASS) and SOFA score. More details about the timing of these parameters are given in appendix 2.
- Microcirculatory value of mitoPO2
- Duration of mechanical ventilation
- Need for renal replacements therapy
- Length of ICU stay
- Length of stay in hospital
- Hospital mortality
- ICU mortality
- 90-day mortality
- Assessment the safety of mitoPO2 measurements
  - Delay of transfusion because of mitoPO2 measurements
  - Adverse and serious adverse events of the mitoPO2 measurements

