### 7.4 Serious adverse events (SAEs)

A serious adverse event is any untoward medical occurrence or effect that

- results in death;
- is life threatening (at the time of the event);

- 
- requires hospitalisation or prolongation of existing inpatients' hospitalisation;
  - results in persistent or significant disability or incapacity;
  - Any other important medical event that did not result in any of the outcomes listed above due to medical or surgical intervention but could have, based upon appropriate judgement by the investigator.

An elective hospital admission will not be considered as a serious adverse event.

The investigator will report all SAEs to the sponsor without undue delay after obtaining knowledge of the events. Patients on the ICU are critically ill and therefore more prone to SAEs. ICU mortality in the Netherlands is approximately 8.4%. Thirty-five percent of the patients are in need for vasopressor therapy, and 46% of the patients are mechanically ventilated. Furthermore, the National Intensive Care Evaluation Report of 2015 reports that the mean ICU admittance duration is 3 days with a mean in hospital admittance duration of 13 days. Around 80% of the total ICU patients have a low APACHE IV score, and therefore a mortality chance of less than 30%. Thus, SAEs in relation to underlying disease and expected SAEs during the ICU course will not be reported.

The coordinating investigator will report the SAEs through the web portal *ToetsingOnline* to the accredited METC that approved the protocol, within 7 days of first knowledge for SAEs that result in death or are life threatening followed by a period of maximum of 8 days to complete the initial preliminary report. All other SAEs will be reported within a period of maximum 15 days after the sponsor has first knowledge of the serious adverse events.

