### **7.8 Data Safety Monitoring Board**

This is a moderate risk study in which the side effect of ALA are well described. The side effects are based on studies with photodynamic therapy. Since the total lightload in photodynamic therapy is significantly higher and longer than during the measurements in this study, no SAEs and SUSARs are

expected. Indeed, studies using the ALA plaster for mitoPO2 measurement in Rotterdam reported no serious adverse events and no SUSARs. These studies were performed on healthy volunteers, surgical patients and patients with chronic anaemia. However, these studies reported local side effects of the ALA plaster consisting of erythema, pruritus and transient hyperpigmentation. All these effects were temporary and disappeared mostly within 1-2 weeks' time. No local side effects or other adverse events were seen in our pilot study. To ensure the safety of our study participants, monitoring will take place during the study. Furthermore, the in- and exclusion criteria are optimised to minimize the risk for participants. Since safety is part of our secondary outcome, we will have attention for AEs, SAEs and SUSARs. With an independent expert on data safety monitoring board confirming the needlessness of a DSMB for the INOX ICU-2 study, no DSMB was initiated.

---

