However, if the patient or legal representative could not have been reached in time for written informed consent, while the patient met the eligibility criteria, patient will be included with deferred consent procedure. Informed consent will be sought within 48 hours after inclusion of the patient. Deferred consent is therefore only used in situations where it is not possible to ask informed consent, including the following: lack of decision-making capacity of the patient due to illness severity, delirium, use of sedatives, analgesics and life-sustaining treatments; inability to contact the legal representative; overwhelming nature of medical information for the legal representative therefore influencing the capability of informed decision-making. At the moment the decision is made to administer a red cell transfusion, the self-adhesive ALA-patch will be placed, if the patient meet the eligibility criteria, and data collection for the study started. Due to logistics, the normal time elapsing between the decision of a non-emergency red cell transfusion and the actual administration is 2 to 3 hours. Therefore, the maximal delay of a non-emergency transfusion will be 1 to 2 hours. To ensure improper delay of red cell transfusion due to the study, the clinician responsible for the patient, and not the researcher, has the final decision in the timing of the red cell transfusion.

If written informed consent was given, but retracted by legal representative or patient after participation, the patient will be excluded and data will no longer be used. If patient or legal representative denies participation during the study, data collected until that time point will be used in the analysis. No further data will be collected.

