### *b. Previous exposure of human beings with the test product(s) and/or products with a similar biological mechanism*

Topical application of ALA is registered for use of photodynamic therapy of skin lesions. Its use for measuring mitoPO2 in healthy volunteers has been proven to be safe in the finished study with protocol number NL37911.078.11 in which the PpIX-TSLT technique was tested on 30 healthy volunteers. All healthy volunteers experienced the skin preparation and measurements as non-problematic. Due to either the skin preparation or the ALA patch, 45% of the volunteers suffered from mild pruritus and/or erythema on the actual measurement day; these minor complaints were no longer present the day after the measurements. Only two volunteers had transient hyperpigmentation of the skin after the measurements, possibly due to premature exposure of the primed area to sunlight (against our advice). The hyperpigmentation was temporary and disappeared within one month. None of the volunteers sustained long-term skin damage, as established one month after the experiments.

It was also used in finished study with protocol number NL56686.091.16 in May and June 2016 at UMC St. Radboud in Nijmegen. This study induced endotoxaemia in human volunteers. Among other measurements, the COMET measurement system and Alacare were used to measure oxygen availability and consumption. ALA was applied on the evening before the endotoxaemia day. The study again confirmed the safety profile of the COMET's measurement also during endotoxaemia. The measurements of the COMET identified change of mitochondrial function in vivo during human endotoxemia.

Other protocols use the same measuring technique: The running studies with Protocol nr: NL51187.078.14 (Photodynamic therapy study) and Protocol nr: NL51937.078.15 (Non-invasive monitoring of mitochondrial oxygen consumption and oxygenation (COMET): observational clinical P16.303

---

study) and NL55664.078.15 (MOTIFATE pilot, a study of blood transfusion and fluid administration in chronic anaemia).

*c. Can the primary or secondary mechanism be induced in animals and/or in ex-vivo human cell material?*

Mitochondrial oxygen tension research has been performed in cells and animals prior to this research proposal. PpIX-TSLT is one of the central techniques used in translational research in the Laboratory of Experimental Anaesthesiology of Erasmus Medical Center.

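### Safety of the mitoPO2 measurement is an outcome, but local reactions are collected passively with no scheduled skin check, so the reported rate has no valid denominator and is biased towards zero

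*Protocol*

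**What the plan says.** Protocol 5.4.2 lists safety of the measurement, including its adverse events, among the secondary outcomes. Section 7.8 repeats this: "Since safety is part of our secondary outcome, we will have attention for AEs, SAEs and SUSARs".

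The collection rule is in 7.3: "All adverse events reported spontaneously by the subject or observed by the investigator or his staff will be recorded". No other rule for finding non-serious events is given:

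- The measurement log in section 4 names skin temperature, vasopressor use and dose, and nurse actions. It does not name the condition of the skin.
- Sections 5.3.1 to 5.3.5 and Appendix 2 contain no skin inspection, symptom question or grading.
- The monitor plan in Appendix 4 checks all subjects for missed events, but for SAEs only.

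On what to expect, section 10(b) reports from the study in 30 healthy volunteers that "45% of the volunteers suffered from mild pruritus and/or erythema on the actual measurement day", and that two had transient hyperpigmentation. Section 7.8 says of this study's own pilot: "No local side effects or other adverse events were seen in our pilot study".

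On the patients, 5.1.1 says that "approximately 10% of critically ill patients can make autonomous decision regarding research participation". Section 8.2 gives among the grounds for deferred consent "lack of decision-making capacity of the patient due to illness severity, delirium, use of sedatives, analgesics and life-sustaining treatments".

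**The concern.** A passive rule depends on someone volunteering a complaint or noticing a sign. Several of the expected reactions are symptoms, and part of this population is sedated, delirious or on analgesics. Error then runs in one direction: a reaction can go unrecorded, whereas a reaction that did not occur is unlikely to be recorded.

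A second problem does not depend on how often patients can speak. If nobody records that the site was inspected and found normal, a patient without an entry may have had no reaction or may not have been checked. The count has a numerator but no defined number of patients assessed.

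At stake is what the safety outcome can support. A low or zero count could be read as evidence that the measurement is well tolerated, when part of it reflects how events were collected. No later analysis can repair this, because the negative findings will not have been collected.

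**Working it through.** The plan gives no reaction rate or precision target for this outcome, so there is no figure to reproduce. The check has three steps.

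**1. What the stated rule can capture**

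| Type of reaction | Examples (7.2, 10(b)) | Route to being recorded | Negative finding recorded? |
|---|---|---|---|
| Visible, up to T5 | erythema, oedema, burn, haemorrhage | seen when the investigator lifts the patch at T0 to T5 | no |
| Symptom | itch, burning sensation, pain | the patient says so unprompted | no |
| First appearing after T5 | e.g. hyperpigmentation | no planned study contact with the site after T5 | no |

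T5 is 24 hours after the end of transfusion (5.3.4). Section 7.8 says local effects mostly disappear within 1 to 2 weeks, and 10(b) says the volunteers' hyperpigmentation disappeared within a month. The volunteer study did establish skin status at one month.

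**2. The pilot zero against the volunteer rate**

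Inputs: 0 of 20 (7.8, 6.1) and 45% of 30 (10(b)). Since 0.45 × 30 = 13.5, both 13 and 14 of 30 are used.

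- If 45% applied and every reaction were detected: P(0 of 20) = 0.55^20 = 6.4 × 10⁻⁶.
- At the exact lower 95% limit of the volunteer rate (25% for 13 of 30, 28% for 14 of 30): P(0 of 20) = 0.003 and 0.001.
- Fisher's exact test of 0/20 against 13/30 or 14/30: p = 0.0006 or 0.0002.
- Upper 95% limit for 0/20: 1 − 0.05^(1/20) = 13.9% one-sided; 1 − 0.025^(1/20) = 16.8% two-sided.
- Hyperpigmentation at 2/30 = 6.7%: P(0 of 20) = 0.25, so a zero there is unremarkable.

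The pilot is therefore not compatible with a 45% rate and full detection.

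**3. Can the pilot separate poor detection from a lower true rate?**

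Recorded rate = true rate × detection sensitivity. The sensitivities below are assumptions. The 189 is the protocol's own target before dropout, used only for scale.

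| Assumed sensitivity | Recorded rate if true rate is 45% | Recorded of 189 | P(0 of 20) |
|---|---|---|---|
| 10% | 4.5% | about 9 | 0.40 |
| 25% | 11% | about 21 | 0.09 |
| 50% | 22.5% | about 43 | 0.006 |
| 75% | 34% | about 64 | 0.0003 |
| 100% | 45% | about 85 | 6.4 × 10⁻⁶ |

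A true 45% with 25% sensitivity gives a recorded rate of 0.45 × 0.25 = 11.25%. So does a true 11.25% with full detection, and both give the same P(0 of 20) = 0.8875^20 = 0.09. The pilot cannot tell these apart. The main study's count would have the same ambiguity under the same rule.

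**The case against.** The strongest reply is that observation here is not left to chance. The investigator performs the measurement (3.1), removes the patch, marks its outline, fixes the sensor and re-covers the skin (section 4), at six planned times. Section 7.3 obliges staff to record what they observe, and 7.7 follows recorded events until they abate or stabilise, so a reaction seen by T5 is not dropped. Many reactions listed in 7.2 are visible. This stands, and it limits the problem for visible reactions up to T5. It does not supply a record that the site was checked and found normal.

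A reader might infer that most patients cannot report. The documents do not say so. The figure of about 10% concerns capacity to decide on research, not ability to mention itch or pain. Section 7.4 gives "46% of the patients are mechanically ventilated" for Dutch ICU patients in general, and cardiothoracic patients are asked for consent the day before surgery, so some may be able to report later.

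A reader might also infer that the pilot zero shows under-recording. It does not. The comparison group was healthy volunteers, 10(i) expects less effect from the newer device because of its lower light dose, and the way the pilot collected events is not shown. Against that, 10(b) attributes the volunteers' complaints to skin preparation or the patch, both of which are used here, and 10(e) still expects mild erythema and pruritus. The light dose may therefore not be the whole explanation, but the question stays open.

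Finally, it would be wrong to say that the absence of a DSMB rests on the pilot zero. Section 7.8 relies on the lower light load, earlier studies of the ALA plaster and an independent expert, and it openly reports local effects in those studies.

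**Conclusion.** The point holds in a limited form. Under the rule in 7.3, with no skin check or symptom question scheduled anywhere, the local reaction rate is biased towards zero and has no valid denominator. The likely losses are symptoms in patients who are sedated or delirious, and effects that first appear after T5. Visible reactions up to T5 have a fair chance of being seen and recorded.

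The size cannot be derived from the documents. The range in the working, about 9 to 85 recorded of 189, rests on carrying over the volunteers' 45% and on assumed sensitivities. It shows how far the result could depend on collection and is not an estimate. The documents do not establish that reactions will be missed or that the measurement is less safe than the protocol says. This is one component of a secondary outcome, concerning reactions that the protocol describes as mild and temporary. It merits a change because the remedy is cheap and must be in place before the data are collected.

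**What to change.** In 7.3 and Appendix 2, add to the existing measurement log:

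- an inspection of the marked patch site at each of T0 to T5, when the patch is off anyway, with yes/no and grade for erythema, oedema, blistering or burn, haemorrhage and pigmentation, recording negative findings as well;
- a question on itch, burning and pain for patients able to answer, with a note of whether the patient could answer.

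Report visible reactions over patients inspected and symptoms over patients asked. Do not present the pilot's zero of 20 as a reaction rate.

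As an option, where the patient is still in hospital, record a later look at the site from routine care. It should stay optional, because after T5 no measurement brings the investigator to the bedside.

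The cost is a few minutes per measurement by someone already present, and possibly a less favourable reported reaction rate.

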### 7.4 Serious adverse events (SAEs)

A serious adverse event is any untoward medical occurrence or effect that

- results in death;
- is life threatening (at the time of the event);

- 
- requires hospitalisation or prolongation of existing inpatients' hospitalisation;
  - results in persistent or significant disability or incapacity;
  - Any other important medical event that did not result in any of the outcomes listed above due to medical or surgical intervention but could have, based upon appropriate judgement by the investigator.

An elective hospital admission will not be considered as a serious adverse event.

The investigator will report all SAEs to the sponsor without undue delay after obtaining knowledge of the events. Patients on the ICU are critically ill and therefore more prone to SAEs. ICU mortality in the Netherlands is approximately 8.4%. Thirty-five percent of the patients are in need for vasopressor therapy, and 46% of the patients are mechanically ventilated. Furthermore, the National Intensive Care Evaluation Report of 2015 reports that the mean ICU admittance duration is 3 days with a mean in hospital admittance duration of 13 days. Around 80% of the total ICU patients have a low APACHE IV score, and therefore a mortality chance of less than 30%. Thus, SAEs in relation to underlying disease and expected SAEs during the ICU course will not be reported.

The coordinating investigator will report the SAEs through the web portal *ToetsingOnline* to the accredited METC that approved the protocol, within 7 days of first knowledge for SAEs that result in death or are life threatening followed by a period of maximum of 8 days to complete the initial preliminary report. All other SAEs will be reported within a period of maximum 15 days after the sponsor has first knowledge of the serious adverse events.

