## 16. Appendix 4: Monitor plan according to NFU-guidelines

Moderate risk but intensive monitoring	
Monitor frequency	3 visits per year per centre
Patientflow	Inclusion speed and percentage of patients fallen out (e.g. withdrawn, loss to follow up)
Trial Master File / Investigator File	Presence and integrity of investigation file
Informed consent	25%
In-/exclusion criteria	25% of all subjects of each centre 
Source Data Verification	25% (Based at predefined list of variables, including primary endpoint, which are in clear relation to safety and validity of the study)
SAE	100% of the total subjects for possible missed SAE. It includes verification of procedures as well. 
Investigated product	Control of instructions given to subjects. Also, control of delivery, distribution, storage, return, expiration date and timely order of the ALA patch
Study procedure	Control of presence of instructions needed for study procedure. If needed, facilities and equipment will be checked as well. An initiation visit will be performed in each centre before start of the study in that centre.
Laboratory	Control of certification of laboratory (GLP certification)
Biological monsters	Control of assemblage, labelling and storage

1 Monitoring of patient flow regardless of the risk classification since inclusion speed going to slow can threaten completion of investigation.

2 If subjects are included wrongly, all files of the centre involved with that will be reviewed and controlled.

3 If the reporting and / or appropriate reporting of serious adverse events (SAE) is incomplete or incorrect, all files of that particular centre need to be checked, regardless of the degree of intensity of monitoring.

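### Section 7.4 both requires and waives SAE reporting, so serious events possibly due to the study's own transfusion delay can escape SAE-level review

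*Protocol*

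**What the plan says.** Three rules stand close together in protocol section 7.4. First: "The investigator will report all SAEs to the sponsor without undue delay after obtaining knowledge of the events". Later in the same paragraph, after figures on background ICU risk: "SAEs in relation to underlying disease and expected SAEs during the ICU course will not be reported". The next paragraph has the coordinating investigator report to the ethics committee "within 7 days of first knowledge for SAEs that result in death or are life threatening", and all other SAEs within 15 days. The exemption does not say to whom the events go unreported, and it does not list the expected events.

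Section 7.3 defines adverse events broadly, "whether or not considered related to the investigational product", and adds: "All adverse events reported spontaneously by the subject or observed by the investigator or his staff will be recorded".

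Section 5.4.2 makes safety a secondary outcome with two items: "Delay of transfusion because of" the mitoPO2 measurements, and "Adverse and serious adverse events of the" same measurements. Section 7.5 defines adverse reactions and SUSARs by the ALA patch. Section 7.6 asks for an annual list of suspected serious adverse reactions, and also for a full safety analysis. Section 7.8 explains that no DSMB was set up. Appendix 4 has monitors check "100% of the total subjects for possible missed SAE".

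**The concern.** Exempting expected ICU events from expedited reporting is common in critical care. Two things make it more than routine here.

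The text does not limit the exemption to expedited reporting. As written, a site may read it as a waiver of all SAE reporting for a class of events that the site itself delimits. Three centres take part and could apply three different rules.

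The study also does something to patients besides applying a patch: it postpones a planned transfusion. If that did harm, the harm would plausibly appear as ischaemia, renal failure or general deterioration, which in an ICU is hard to tell from underlying disease. The exemption keeps no reporting duty for serious events that may be due to a study procedure. At stake are case-by-case causality assessment and timely review by someone outside the bedside team.

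**Working it through.** There is no stated figure to reproduce. The check sets the passages side by side and follows one hypothetical event: life-threatening renal failure some hours after a delayed transfusion, which the site regards as part of the underlying illness.

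**1. The three rules in 7.4**

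| Rule | Recipient | Exception stated | Result for this event |
|---|---|---|---|
| All SAEs | Sponsor | None | Reported |
| Disease-related or expected SAEs | Not named | It is the exception | Not reported |
| Fatal or life-threatening SAEs | Ethics committee | None | Reported within 7 days |

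The three results cannot all hold. Section 7.7 adds that SAEs must be reported until the end of the study, again without an exception.

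**2. Is the delay a study procedure?** Section 5.1.1 puts the usual time from decision to transfusion at 2 to 3 hours and the patch induction time at 4 hours or more. The added delay is 4 − 3 = 1 hour to 4 − 2 = 2 hours, as the protocol states.

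**3. Which other routes would catch the event?**

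- 7.3: recorded as an adverse event if observed. Recording alone sends it nowhere.
- 7.5: not a SUSAR unless a reaction to the patch is probable. The trigger for discussing termination (2 or more SUSARs in 6 months) therefore does not count it.
- 7.6, first item: lists suspected serious adverse reactions, so does not require it.
- 7.6, second item: a complete safety analysis could include it, but the content is not fixed.
- 7.1 and 9.4: the duty to act on greater-than-foreseen disadvantages, and the yearly note of unexpected problems, are not limited to the patch. Both depend on someone having seen a pattern.
- 5.3.2, 5.3.3 and 5.4.2: death, renal replacement, creatinine, troponin, RIFLE and SOFA are collected whatever the SAE status. Section 5.3.4 records the delay. One gap is that section 5.2 ends follow-up for withdrawn subjects, including those withdrawn for urgent medical reasons.

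The event would be visible in the data, but nothing guarantees an SAE report or a causality judgement.

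**4. Monitoring.** Under footnote 3 of Appendix 4, incomplete or incorrect SAE reporting at a centre means that all its files are checked. Under the first rule in the table, an unreported disease-related SAE is such a failure. Under the second, it is compliant.

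**5. What could full reporting show?** Inputs: 209 patients (6.1) and 8.4% ICU mortality (7.4), treated as a benchmark only for this step. Expected ICU deaths are 209 × 0.084 = 17.6. The smallest count with an exact one-sided binomial tail of at most 0.025 is 27 (tail 0.017). For assumed true mortality of 10%, 12%, 14% and 16%, the chance of reaching 27 is 10%, 37%, 70% and 91%. Even a complete count would reveal only a large excess, and with no undelayed group it could not assign that excess to the delay.

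**The case against.** The strongest reply is that 7.4 has a natural reading. The first sentence names the sponsor. The exemption follows a description of background ICU risk and directly precedes the ethics-committee paragraph, whose SAEs can be taken as those left after the exemption. On that reading everything goes to the sponsor, and only expected ICU events are kept from the committee. This is plausible and sensible, but the text does not say it.

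It can also be said that the delay is tightly limited. Emergency transfusions are excluded, the treating clinician decides the timing, and no delay is allowed when transfusion is clinically needed. An event judged to be caused by the delay is not, on its face, disease-related. The animal data in the introduction (kidney failure after 2 hours without transfusion) concern haemodilution to a predefined mitoPO2 fall, not a logistical delay in patients. All this stands, and it means that harm from the delay is a possibility, not something the protocol shows. It does not settle who makes that judgement when the site has already classed the event as expected.

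Some stronger readings are tempting and are not supported:

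- That the safety outcome cannot show harm from the delay. The delay, adverse events, deaths and organ markers are all collected and can be tabulated together.
- That exempt events reach no safety summary. Section 7.6 also asks for a complete safety analysis, and section 7.1 is not confined to the patch.
- That about 18 deaths measure the problem. The 8.4% is general Dutch ICU mortality over a whole stay, not that of this transfused cohort, and every ICU death is counted as an outcome anyway.
- That monitors cannot do their check. They can, but against an unclear standard.

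**Conclusion.** The contradiction in 7.4 is plain from the text. Followed as written, the exemption can remove serious events possibly related to the transfusion delay from SAE reporting and causality review, and the product-based routes in 7.5 and the reaction list in 7.6 do not replace them. With no DSMB, that review is worth having.

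The consequence is moderate. Harm would not be invisible, and attribution would remain limited under any SAE rule. The number of events affected cannot be derived from the protocol. The conclusion assumes only that some sites would take the exemption at its word, and that some delay-related events would resemble underlying disease. It does not assume that the delay is harmful.

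**What to change.** Reconcile the sentences in 7.4 by stating that:

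1. the exemption applies only to expedited reporting to the ethics committee;
2. all SAEs from patch placement to T5 are recorded and sent to the sponsor as a line list;
3. SAEs judged possibly related to any study procedure, including the transfusion delay, are never exempt;
4. the line list is tabulated beside the recorded delay in the annual safety report under 7.6.

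Then align the missed-SAE check in Appendix 4 to the same definition, so that monitors and sites work to one rule.

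The cost is slightly more investigator paperwork. With 4 hours of patch induction, a 1-hour transfusion and T5 at 24 hours after its end, the window is about 4 + 1 + 24 = 29 hours per patient, longer if induction or transfusion takes longer. Deaths, organ markers and the delay are already collected. No clinical rule changes.
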